8.0 Statistical Considerations

This study has two specific aims: to examine how many patients continue to maintain their LVEF after discontinuing HF medications (beta-blockers, ACE-I and/or ARBs) for 6 months while enrolled in the study and to describe the characteristics of patients who successfully maintain their LVEF and those who have a decrease in their LVEF during the weaning process and after discontinuing HF medications.

Failure is defined as an LVEF < 50%, or > 10% decrease from baseline LVEF or occurrence of any cardiac related adverse events including acute coronary syndrome, malignant ventricular dysrhythmias (e.g. ventricular tachycardia or ventricular fibrillation) or new onset atrial fibrillation or atrial flutter. Incidences of premature discontinuation from the study because of a decrease in the participant's LVEF will be considered a HF medication withdrawal failure. Patients who discontinue early for reasons not related to heart failure will be replaced. We anticipate only a 20% failure rate. Failure rate, and its corresponding 90% confidence interval, will be calculated separately for each stratum, and this information will be used to plan a larger, confirmatory controlled trial. If the failure rate is 20%, the 90% confidence interval will extend from 13% to 37%.

We will also describe characteristics of participants who have a decrease in their LVEF and those who maintain their LVEF using means, standard deviations, graphs and contingency tables. We will examine risk factors, such as increased troponin I, and B-type natriuretic peptide concentrations or abnormal echocardiographic strain that increase the possibility of withdrawal failure, as well as other clinical/demographic factors, as described in Sections 4 and 5. No hypothesis testing will be completed. The study results will be used to calculate power and sample size for the planning of a larger confirmatory trial.

Sample Size: The study will include 45 cancer survivors who meet the inclusion criteria, are followed up in the MD Anderson Cancer Center cardiology clinic, and agree to participate in the study. Patients will be stratified by type of chemotherapy, enrolling 15 patients who were treated for their cancer with anthracyclines, 15 who were treated with Herceptin, and 15 who were treated with a combination of agents or who had HF secondary to sepsis or stress induced cardiomyopathy.

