2. Collection of blood specimen for laboratory works (BNP, Troponin I, Electrolytes (Sodium, Potassium, Chloride, CO₂), BUN, Creatinine).
3. 2-D echocardiogram with contrast to measure LVEF and strain and evaluate for early signs of change in cardiac function.
4. Symptom assessment using the MDASI-HF instrument.

Heart failure will be defined as an LVEF < 50%, or a decrease of >10% from baseline LVEF, at any time during the weaning and after completely off of HF medications while enrolled in the study.

The baseline and follow up echocardiograms will be interpreted by the same two cardiologists who are collaborators in the study to ensure consistency of interpretation. If the participants' echocardiography reveals a decrease in the LVEF (<50% or >10% lower than baseline LVEF), the attending cardiologist will be notified immediately, and the participant will be evaluated if they have met the

endpoint considered as failure for the study. The participant will be carefully monitored, and HF medication will be titrated as clinically indicated and followed closely as clinically necessary until LVEF return to baseline and symptoms resolved.

If the participant develops HF symptoms even with normal LVEF from previous echocardiogram during a regular follow up per study protocol, an echocardiogram may be repeated as clinically indicated at any time point in addition to the study time points. Should the LVEF drop after the HF medications has been completely discontinued, the attending cardiologist will be notified and HF medications will be restarted and gradually uptitrated until normal baseline LVEF is achieved.

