6.0 Criteria for Removal from the Study

On the basis of clinical observation and the experience of clinicians involved in the management of CILVD, we predict that 20% of the participants will experience a decrease in their LVEF when the HF medications are completely discontinued. The demographic characteristics, types of prior chemotherapy received, total dosage of chemotherapy (for participants previously treated with anthracyclines), cardiac biomarkers (i.e. BNP, troponin I), and echocardiography findings of these participants will be identified.

The participants will be removed from the study if any of the following conditions occur:

- 1) Echocardiography which reveals a decrease in the LVEF (<50% or >10% lower than baseline LVEF).
- 2) Occurrence of any cardiac related adverse events including acute coronary syndrome, malignant ventricular dysrhythmias (e.g. ventricular tachycardia or ventricular fibrillation) or new onset atrial fibrillation or atrial flutter.
- 3) Patients that cannot tolerate weaning of HF medications because of hypertension or increased pulse rate will be removed from the study and replaced.

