7.0 Protocol Monitoring

To ensure patient safety, we will implement continuous monitoring for excessive heart failure using a design developed by Thall, et. al.,(1995). Specifically, we will terminate enrollment into a particular stratum if $Pr[\pi_{HF} > 0.20 | \text{data}] > 0.92$. To

use this rule, we will assume that π_{HF} has a prior distribution of $B(0.4, 1.6)$. The rule will be applied separately to each stratum because we are concerned that response will not be homogenous across strata. Table 3 gives the specific stopping rules, and Table 4 has the operating characteristics of this rule. Tables 3 & 4 were developed using a Stata program designed by [name].

Table 3. Rules for stopping for excessive occurrence of heart failure

# of Patients with Heart Failure	# of Patients Enrolled in Stratum
3	5
4	6, 7, 8, or 9 patients
5	10, 11, or 12 patients
6	13, 14, or 15 patients

Table 4. Operating Characteristics of Early Stopping Rule

P(True Toxicity Rate)	P(Stop Early)	p10	p25	p50	p75	p90	Avg # pts	Avg # toxicities
0.10	0.0156	15	15	15	15	15	14.87	1.46
0.15	0.0551	15	15	15	15	15	14.57	2.18
0.20	0.1284	9	15	15	15	15	14.03	2.76
0.25	0.2365	7	15	15	15	15	13.25	3.31
0.30	0.3772	5	9	15	15	15	12.21	3.67
0.40	0.6561	5	5	9	15	15	9.92	3.97
0.50	0.8620	5	5	7	9	15	7.93	3.94

To illustrate this stopping rule, let's say that 10 patients have been enrolled in a particular stratum and that only 4 have had heart failure. The 11th patient is now enrolled and he/she develops heart failure. Enrollment to this stratum will be terminated because $\Pr[\pi_{HF} > 0.20 \mid \text{data}] = 0.96$. Under this stopping rule, we will terminate enrollment early 13% of the time when the proportion of patients who have subsequent heart failure is truly 20%. We will terminate enrollment early 86% of the time when the proportion of patients who have subsequent heart failure is 50%. It should be noted that the stopping rule will be applied for a decrease in LVEF (<50% or >10%

decrease from baseline LVEF), or occurrence of any cardiac related adverse events including acute coronary syndrome, malignant ventricular dysrhythmias (e.g. ventricular tachycardia or ventricular fibrillation) or new onset atrial fibrillation or atrial flutter. These conditions will count as failure for both the primary endpoint and for the safety monitoring rule.

Data management

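### Replacing participants who leave event-free, with no time cut-off and no stated denominator, can inflate each stratum's failure rate if leaving is unrelated to failure risk

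*Combined protocol and SAP*

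**What the plan says.** Section 8.0 sets 15 participants in each of three strata and treats exits in two ways. An exit for falling LVEF is an outcome: "Incidences of premature discontinuation from the study because of a decrease in the participant's LVEF will be considered a HF medication withdrawal failure". An exit for another reason is refilled: "Patients who discontinue early for reasons not related to heart failure will be replaced". Section 6.0 adds a second replacement rule: "Patients that cannot tolerate weaning of HF medications because of hypertension or increased pulse rate will be removed from the study and replaced".

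The estimator is a simple proportion: "Failure rate, and its corresponding 90% confidence interval, will be calculated separately for each stratum". No analysis set, censoring rule or method for partial follow-up is given.

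The time horizon is not fixed. Section 5.0 counts an LVEF decrease "at any time during the weaning and after completely off of HF medications while enrolled in the study", and Table 1 runs to Month 30. The opening of Section 8.0 frames the aim over 6 months.

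Sections 7.0 and 8.0 also count the listed cardiac events as failures. Section 7.0 says: "These conditions will count as failure for both the primary endpoint and for the safety monitoring rule". Table 3 is indexed by the number enrolled in the stratum and ends at 15.

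**The concern.** The two kinds of exit are not treated alike. A participant whose LVEF falls at Month 4 stays in the rate permanently. A participant whose LVEF is maintained at Months 2 and 4, and who then moves away, gives the place to a newcomer who starts again at full risk. If the leaver's data are dropped, the 15 counted are those who failed before leaving plus those who stayed to the end. Follow-up without failure is then lost selectively.

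The stratum failure rate is the plan's main estimate and is meant to inform the size of the confirmatory trial. A larger pilot would reduce sampling error but would not remove this shift. Refilling places also withdraws medication from additional survivors when part of the leaver's outcome was already known.

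**Working it through.** **Inputs.** From Section 8.0: 15 per stratum and an anticipated failure rate of 20%. Assumed, because the documents give nothing: a proportion d = 10%, 20% or 30% who would leave for unrelated reasons during the follow-up window.

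**The plan's own figures.** For 3/15 the standard error is √(0.2 × 0.8/15) = 0.103. The 90% Wald limits are 0.2 ± 1.645 × 0.103, or 3.0% to 37.0%. Section 8.0 gives 13% to 37%. The upper limit reproduces. The lower limit does not, either here or by Wilson (8.3% to 40.9%) or Clopper-Pearson (5.7% to 44.0%). That is a separate matter, and the interval serves here only as a yardstick. For Table 4 at a true 20%, an exact recursion on the Table 3 boundaries, with looks after patients 5 to 14, gives an early-stopping probability of 12.9% against the stated 0.1284.

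**Formula.** Let A be the probability of failing before leaving, and B the probability of neither failing nor leaving. If leavers are replaced and their data dropped, the expected rate among those counted is A/(A + B). Filling 15 places takes 15/(A + B) enrolments. Early stopping is ignored.

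- Constant hazards: λ = −ln 0.8 = 0.223, μ = −ln(1 − d), A = λ/(λ + μ) × [1 − 0.8(1 − d)], B = 0.8(1 − d).
 - d = 10%: 0.190/(0.190 + 0.72) = 20.9%
 - d = 20%: 0.180/(0.180 + 0.64) = 22.0%
 - d = 30%: 0.169/(0.169 + 0.56) = 23.2%
- Upper bound, all failures before any leaving: A = 0.2, with B as above.
 - d = 10%: 0.2/0.92 = 21.7%
 - d = 20%: 0.2/0.84 = 23.8%
 - d = 30%: 0.2/0.76 = 26.3%
- Lower bound, all failures at the end: A = 0.2(1 − d), so the rate stays at 20.0%.
- Constant hazards over 6 months, with failures found only at the Month 2, 4 and 6 echocardiograms: A is the sum over the three intervals of failing in that interval and still being enrolled at its echocardiogram.

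| Assumed d | Lower bound | Echo visits only | Constant hazards | Upper bound | Enrolled to fill 15 (constant hazards; upper bound) |
|---|---|---|---|---|---|
| 10% | 20.0% | 20.6% | 20.9% | 21.7% | 16.5; 16.3 |
| 20% | 20.0% | 21.3% | 22.0% | 23.8% | 18.3; 17.9 |
| 30% | 20.0% | 22.2% | 23.2% | 26.3% | 20.6; 19.7 |

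**Does the direction hold if leaving is related to risk?** Spread failures evenly over 6 months and let would-be failers leave at m times the hazard of the others. Then A = 0.2 × (1 − e^(−mμ))/(mμ). At m = 2 the rate is 20.0% (d = 10%) or 20.1% (d = 20%), so the bias is gone. At m = 3 it is 19.2% or 18.6%, below the truth.

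**Replacement for weaning intolerance (Section 6.0).** If a share s of participants is replaced and carries twice the failure risk of the rest, the retained rate is 0.2/(1 + s). That is 18.2% at s = 10% and 16.7% at s = 20%. Both the share and the doubled risk are assumptions.

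**Stopping rule.** If only retained participants count in Table 3, early stopping at a true 20% rises from 12.9% to 14.6% (d = 10%) or 16.8% (d = 20%) under constant hazards.

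**Alternatives.** Keeping all enrolled and censoring leavers by Kaplan-Meier gives 20.0% to 20.3% in simulation when leaving is unrelated to risk. Keeping leavers in a raw proportion as non-failures gives A itself, 18.0% at d = 20%, which is too low.

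**The case against.** **Exclusion is inferred.** The documents never say that replaced participants leave the analysis. That is true. But a fixed 15 per stratum, a replacement rule and a raw rate make it the natural reading, and nothing in the plan offers another.

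**A reader might infer that the rate is certainly biased upward.** The documents do not support that. It needs leaving to be unrelated to failure risk, and replacement of weaning-intolerant participants may push the other way. The net direction is unknown.

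**A reader might infer that 12 or 18 months of success off medication is thrown away.** That takes Month 30 as the horizon. Section 8.0 also names 6 months, and someone who has passed that point need not have left early. The upper-bound figures carry most weight if later leavers are replaced. The replacement sentence leaves this open.

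**A reader might infer that participants removed for acute coronary syndrome or atrial fibrillation with preserved LVEF are replaced,** because Section 5.0 defines heart failure by LVEF alone. Sections 7.0 and 8.0 both count these events as failures, and no text says that such participants are replaced. The wording is loose. Replacing them would discard failures and bias the rate downward.

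**The shift is small.** This stands. Under constant hazards it is 0.9 to 3.2 points, or 0.14 to 0.48 of a patient in 15. One patient is 6.7 points and the standard error is 10.3 points. No hypothesis test is planned.

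**Conclusion.** The concern holds in conditional form. Replacement without a cut-off, combined with a raw rate and no rule for replaced participants, discards event-free follow-up if those participants leave the denominator. Where leaving is unrelated to risk, a true 20% is then reported on average as about 21% to 23% (constant hazards, 10% to 30% leaving), and as at most about 22% to 26%. Under the same assumptions, about 16 to 21 people per stratum would be enrolled to fill 15 places.

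These sizes rest on dropout rates that the documents do not give. The shift is minor beside the sampling error and would vanish or reverse if would-be failers left at two to three times the hazard of others. The plan should still be changed, because the denominator is undefined, the estimate feeds the next trial, and a better estimator costs little.

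**What to change.** - Keep every participant who starts weaning in the stratum's analysis, whether or not replaced.
- Fix one landmark and its time origin. Section 8.0 names 6 months off medication. Weaning starts on Day 1 and is expected to take about 6 weeks, so 6 months off falls near Month 7.5, between the Month 6 and Month 12 echocardiograms. The plan should say which assessment decides the outcome.
- Report the failure proportion at the landmark, with its 90% interval, by Kaplan-Meier, or by cumulative incidence with non-cardiac death as a competing event. Censor event-free leavers at their last echocardiogram.
- State that participants who leave after the landmark are not replaced, and that those removed for the listed cardiac events, already failures in Sections 7.0 and 8.0, are not replaced.
- State how replaced participants, including the weaning-intolerant ones in Section 6.0, count in the estimate and in Table 3, and what applies if enrolment in a stratum passes 15.
- Report the number replaced and the reasons, with a sensitivity analysis in which leaving is related to risk.

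The cost is a few sentences in Sections 6.0, 7.0 and 8.0 and a standard estimator. If fewer participants are replaced, a stratum may have fewer than 15 with complete follow-up. The new estimate still assumes non-informative censoring, which is why the sensitivity analysis is needed.

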1.0 Objectives

The overall goal of this pilot study is to examine whether cancer survivors with a history of cancer-induced left ventricular dysfunction (CILVD) resulting in heart failure (HF) who achieve left ventricular ejection fraction (LVEF) recovery with recommended HF medications for at least 6 months will maintain their LVEF if HF medications are discontinued. The findings from this pilot study will provide baseline information for planning a larger confirmatory trial to support evidenced- based practice for the pharmacological management of cancer survivors with a history of CILVD.

Specific Aim 1: To determine the percentage of cancer survivors that can maintain their LVEF after discontinuing HF medications (beta blockers, angiotensin converting enzyme inhibitors (ACE-I), or angiotensin receptor blocker (ARB)).

Specific Aim 2: To describe the characteristics of cancer survivors who successfully maintain their LVEF and those whose LVEF decrease as measured by an echocardiogram with contrast after they discontinue HF medications.

The **primary endpoint** for this pilot study is a decrease in the LVEF when HF medications are discontinued, and the **secondary endpoints** are the changes in the cardiac biomarkers, such as increased troponin I, B-type natriuretic peptide (BNP) or abnormal strain on echocardiogram that can predict the possibility of HF medication withdrawal failure. The cardiac biomarkers (troponin I, BNP) and abnormal strain on echocardiogram are early indicators of myocardial injury.

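### Aim 1 asks for one percentage of cancer survivors, but the plan sets out no overall estimate with an interval, only three rates on 15 patients each

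*Combined protocol and SAP*

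**What the plan says.** Specific Aim 1 in Section 1.0 reads "To determine the percentage of cancer survivors that can maintain their LVEF after discontinuing HF medications", and it does not mention strata. Section 8.0 restates the aim as a count of patients who maintain LVEF, again without strata.

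The only planned estimate with an interval is by stratum: the failure rate and its 90% confidence interval "will be calculated separately for each stratum, and this information will be used to plan a larger, confirmatory controlled trial". The sample size is set the same way. "The study will include 45 cancer survivors who meet the inclusion criteria", and "Patients will be stratified by type of chemotherapy, enrolling 15 patients who were treated for their cancer with anthracyclines", with 15 more treated with Herceptin and 15 in a third group that combines several causes. The planning assumption is "We anticipate only a 20% failure rate", and the precision statement is "If the failure rate is 20%, the 90% confidence interval will extend from 13% to 37" per cent.

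The reason for separating strata appears in Section 7.0 and concerns the stopping rule: "The rule will be applied separately to each stratum because we are concerned that response will not be homogenous across strata".

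**The concern.** The aim and the analysis are set at different levels. The aim is about cancer survivors with recovered LVEF as one group, while the analysis gives three rates and stops there. Concern about heterogeneity is a sound reason to monitor and report strata separately. It does not explain why the quantity named in the aim has no planned estimate and interval.

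Two things are at stake. Each stratum rate rests on about three expected failures (15 × 0.20 = 3), so the planned intervals are very wide. Readers are also likely to combine the strata anyway. Without a stated method, the weights, the interval and the treatment of a stratum closed early would be chosen after the data are seen.

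**Working it through.** **Inputs.** Section 8.0 gives 15 patients in each of three strata (45 in total), an anticipated failure rate of 20% (3/15 per stratum, 9/45 overall) and 90% confidence (z = 1.645). Table 4 in Section 7.0 gives a probability of early stopping of 0.1284 per stratum at a true rate of 20%.

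**1. The plan's own interval.** The Wald formula is p ± z√(p(1−p)/n). For 3/15 it gives 0.20 ± 1.645 × √(0.16/15) = 0.20 ± 0.170, or 3.0% to 37.0%. The printed upper limit of 37% agrees with this; the printed lower limit of 13% does not. Wald, Wilson, exact, Jeffreys and several other methods, tried at n = 15, 30 and 45 and at 80%, 90% and 95% confidence, did not reproduce 13% to 37% at a 20% rate. The 13% looks like a misprint of 3%, though that is an inference. The printed width of 24 points is therefore not a valid benchmark for a stratum of 15.

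**2. Stratum against overall, 90% intervals at 20% failure.**

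| Method | 3/15 | Width (points) | 9/45 | Width (points) | Ratio |
|---|---|---|---|---|---|
| Wald | 3.0% to 37.0% | 34.0 | 10.2% to 29.8% | 19.6 | 0.58 |
| Wilson | 8.3% to 40.9% | 32.6 | 12.0% to 31.4% | 19.4 | 0.59 |
| Exact (Clopper-Pearson) | 5.7% to 44.0% | 38.3 | 10.9% to 32.3% | 21.5 | 0.56 |
| Jeffreys | 7.6% to 40.2% | 32.6 | 11.7% to 31.1% | 19.3 | 0.59 |

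The Wald ratio is 1/√3 = 0.577 by construction.

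**3. The estimator proposed under the fix.** The equal-weighted average is (p₁ + p₂ + p₃)/3, with variance (1/9) Σ pᵢ(1−pᵢ)/nᵢ. With 3/15 in each stratum, the variance is (1/9) × 3 × 0.16/15 = 0.003556 and the standard error is 0.0596. The interval is 0.20 ± 1.645 × 0.0596, or 10.2% to 29.8%.

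The formula does not require equal rates. With assumed true rates of 10%, 20% and 30% the width is 19.2 points, and with 5%, 20% and 35% it is 18.7 points.

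**4. Early stopping.** If the strata are independent and each has a true rate of 20%, the chance that at least one stops early is 1 − (1 − 0.1284)³ = 0.338, about 34%.

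As an assumed illustration, suppose one stratum stops at 3/5, as Table 3 allows, and the other two finish at 3/15. The equal-weighted average is (0.60 + 0.20 + 0.20)/3 = 33.3%, while simple pooling gives 9/35 = 25.7%. The stratified variance is (1/9)(0.24/5 + 0.16/15 + 0.16/15) = 0.00770. The equal-weighted width is then 2 × 1.645 × √0.00770 = 28.9 points. The choice of estimator matters in this case, so it should be fixed in advance.

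**5. Failure is not the complement of LVEF maintenance.** Sections 7.0 and 8.0 count acute coronary syndrome, malignant ventricular dysrhythmias and new atrial fibrillation or flutter as failure. A participant with one of these events and a preserved LVEF is a failure but has not lost LVEF. One minus the failure rate is therefore not exactly the percentage in Aim 1.

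**The case against.** The strongest reply is that the stratum-only analysis is deliberate. Enrolment, sample size and stopping are all set by stratum, and heterogeneity is an explicit worry. That worry is voiced for the stopping rule, but it fits the analysis equally well. The study is a pilot with no hypothesis tests. An equal-weighted average also gives one third of the weight to a group that mixes combination therapy with sepsis-related and stress-induced cardiomyopathy, so it describes no natural population. This stands as a reason to keep the stratum rates first and to label the overall rate with its weighting. It does not justify leaving the aim without an estimate.

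A reader might infer that the study will yield nothing that answers Aim 1. The documents do not support that. With full quotas, the overall point estimate is the average of the three reported rates, and Section 8.0 also plans descriptive tables of those who do and do not maintain LVEF. What is absent is a prespecified overall estimate with its interval.

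A reader might also infer that the confirmatory trial must be sized from three imprecise rates. Section 8.0 says more generally that the study results will be used for power and sample size, so planners could combine the counts. They would have no agreed method for doing so.

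**Conclusion.** The point holds as a mismatch between the aim and the planned analysis: no overall estimate with an interval is prespecified for a question put about one group. At a 20% failure rate with all strata complete, an overall interval is 56% to 59% as wide as a stratum interval, a reduction of roughly 42%. It would be tempting to say that the width is halved, but none of the four methods gives that. Comparing with the printed 13% to 37% would instead understate the gain (19.6/24 = 0.82), but that interval does not correspond to 15 patients at 20%.

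The size of the gain assumes 15 patients in each stratum and an overall rate near 20%. It does not depend on the strata sharing a rate, but it shrinks if a stratum closes early. The exact 9/45 interval treats the participants as one sample. It shows the scale of the gain and is not the interval for the equal-weighted estimator. Participant safety and the stopping rule are not affected.

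**What to change.** Keep the stratum rates and stratum monitoring as they are, and add the following to Section 8.0:

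- A supplementary overall estimate: the equal-weighted average of the three stratum rates, with a 90% interval from the stratified variance, reported after the stratum results.
- A statement that each stratum keeps weight one third if it closes early, with its variance based on the number actually enrolled. The named interval method should also cope with a stratum that has no failures, because the Wald variance for that stratum is then zero.
- Two separately defined overall quantities: the composite failure rate and the percentage maintaining LVEF. The second needs a rule for participants removed under Section 6.0 for a cardiac event while LVEF was preserved.
- A sentence saying that the overall figure reflects the 15:15:15 quota, including the mixed third stratum, and is secondary if the strata clearly differ.
- A corrected precision statement in place of 13% to 37%, naming the interval method and the sample size.

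The cost is a few lines of text and one extra calculation, with no change to enrolment, visits or monitoring. There are two downsides. The overall figure does not describe the clinic's natural mix. Equal weighting also gives a stratum stopped early for many failures more influence than pooling would, as the illustration shows.

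### The stated 90% confidence interval of 13% to 37% at a 20% failure rate does not follow from 15 patients per stratum; the lower limit is wrong and no interval method is named

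*Combined protocol and SAP*

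**What the plan says.** Section 8.0 fixes every input needed to check the figure.

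- Unit of analysis: "Failure rate, and its corresponding 90% confidence interval, will be calculated separately for each stratum".
- Anticipated rate: "We anticipate only a 20% failure rate".
- Stratum size: "enrolling 15 patients who were treated for their cancer with anthracyclines, 15 who were treated with Herceptin, and 15 who were treated with a combination" (the third stratum also takes heart failure secondary to sepsis or stress-induced cardiomyopathy).
- Resulting precision: "If the failure rate is 20%, the 90% confidence interval will extend from 13% to 37" per cent.

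The same section rules out hypothesis tests and says what the estimates are for: "The study results will be used to calculate power and sample size for the planning of a larger confirmatory trial". Patients who leave early for reasons unrelated to heart failure are replaced, so the planned denominator stays at 15. No method for the confidence interval is named in Section 8.0 or elsewhere in the document.

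**The concern.** The printed interval reaches 7 points below 20% and 17 points above it. A normal-approximation interval would be symmetric. The methods that are asymmetric at this sample size have lower limits well under 13%. So the two limits do not appear to belong to the same calculation.

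The study estimates and does not test, and this sentence is the only statement of how precisely a stratum's failure rate will be known. It implies that 3 failures in 15 would exclude true rates below 13%. Fifteen patients cannot do that: at a true rate of 10%, three or more failures in 15 occur about 18% of the time. The error makes the pilot look more informative than it is.

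The missing method is a second gap. At this sample size the choice visibly changes the reported result, and the plan leaves it open until the data are in.

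**Working it through.** **Inputs (Section 8.0).** Rate p = 0.20; n = 15 per stratum, so x = 3; two-sided 90% level, z = 1.645.

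**Attempt to reproduce the printed 13% to 37%.**

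*Wald:* p ± z·√(p(1−p)/n). The standard error is √(0.20 × 0.80 / 15) = 0.1033 and the half-width is 1.645 × 0.1033 = 0.170. Limits: 0.20 ± 0.170 = 3.0% to 37.0%. The upper limit matches the plan; the lower does not.

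*Wilson:* centre (p + z²/2n)/(1 + z²/n) = (0.20 + 0.0902)/1.1804 = 0.2458. Half-width z·√(p(1−p)/n + z²/4n²)/(1 + z²/n) = 1.645 × √(0.01067 + 0.00301)/1.1804 = 0.163. Limits: 8.3% to 40.9%.

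*Exact (Clopper-Pearson):* the 5th percentile of Beta(3, 13) and the 95th percentile of Beta(4, 12). Limits: 5.7% to 44.0%.

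| 90% interval | 3/15 | Width (points) | 9/45 (pooled) |
|---|---|---|---|
| As printed | 13% to 37% | 24 | – |
| Wald | 3.0% to 37.0% | 34.0 | 10.2% to 29.8% |
| Wilson | 8.3% to 40.9% | 32.6 | 12.0% to 31.4% |
| Exact | 5.7% to 44.0% | 38.3 | 10.9% to 32.3% |
| Jeffreys | 7.6% to 40.2% | 32.6 | 11.7% to 31.1% |
| Agresti-Coull | 7.8% to 41.4% | 33.7 | 11.9% to 31.5% |
| Mid-p | 7.0% to 41.1% | 34.1 | 11.6% to 31.2% |
| Logit | 8.0% to 42.0% | 34.0 | 11.9% to 31.6% |

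Widths are taken from the unrounded limits. Across fourteen variants at 3/15 (adding continuity-corrected, n−1, t-based, log, arcsine and two Bayesian intervals), the highest lower limit is 9.0%, from a uniform prior. Section 7.0 specifies a Beta prior for safety monitoring ("has a prior distribution of $B(0.4, 1.6"). With 3/15 the posterior is Beta(0.4 + 3, 1.6 + 12) = Beta(3.4, 13.6), whose 90% credible interval is 6.7% to 37.4%. It also rounds to 37% at the top, but its lower limit is 7%.

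**Could another sample size explain it?** Holding the rate at 20%, no tested method gives 13% to 37% at any n from 5 to 200. A 90% lower limit that rounds to 13% first appears at n = 50 (n tested in steps of 5), where the upper limit is only 31% to 32%. Solving the Wald formula for each printed limit separately:

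- lower limit 13%: n = 0.16 × (1.645/0.07)² ≈ 88
- upper limit 37%: n = 0.16 × (1.645/0.17)² ≈ 15

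The upper limit fits the planned stratum size and the lower limit does not. Putting 3% in place of 13% restores the Wald interval at n = 15.

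**Does the choice of method matter at n = 15?** Coverage at a true rate of 20% is the binomial probability of those counts whose interval contains 20%. The Wald interval misses at 0 or 1 failures (0.035 + 0.132 = 0.167) and at 7 or more (0.018), so it covers 1 − 0.185 = 81.5%. Wilson covers 90.4% and exact 94.7%. Over true rates of 10% to 40%:

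| Method | Minimum | Mean | Maximum |
|---|---|---|---|
| Wald | 72.8% | 84.9% | 91.6% |
| Wilson | 84.1% | 90.5% | 96.8% |
| Exact | 90.9% | 95.2% | 98.7% |

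**The case against.** The strongest objection is about weight. The sentence is an illustration. The confirmatory trial will be planned from the observed rate and its interval, and no decision rule uses 13%. In a withdrawal study the upper limit is the one that matters most, and 37% is correct under Wald. The stopping rule has its own basis in Section 7.0: "Table 3 gives the specific stopping rules, and Table 4 has the operating characteristics of this rule". Every boundary in Table 3 lies at an observed rate of 40% or more (the lowest is 6/15), so it is untouched. All of this stands and limits the consequence. It does not make the printed figure right.

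The second objection is about cause. The range 13% to 37% is symmetric about 25%, and the Wald interval for 9/36 rounds to exactly those limits, so the sentence could be left over from a different assumed rate and sample size. That cannot be excluded. But neither 25% as an anticipated rate nor 36 as a sample size is a design value in the document, and 3% to 37% needs only one stray digit at the plan's own rate and n. A digit introduced when the PDF was read is also conceivable, although the sentence is intact running text; the sponsor can settle this against the source file. The misprint explanation therefore remains an inference.

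The third objection is that preferring Wilson or exact over Wald is a choice of method and not an arithmetic correction. That is fair, and the two are kept apart in the recommendation. Naming some method is needed in either case.

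**Conclusion.** The concern holds. With 15 patients per stratum and a 20% failure rate, the lower 90% limit is between about 2% and 9% for every untruncated variant tried, except the continuity-corrected Wald, which falls just below zero. It is not 13%. The printed width of 24 points understates the uncertainty by about 9 points (Wilson), 10 (Wald) or 14 (exact). For the same 3/15 the upper limit would be 37% by Wald, 41% by Wilson and 44% by exact, so the unnamed method also matters.

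The conclusion rests on the plan's own inputs: 90% level, 20% rate, per-stratum analysis and 15 evaluable patients per stratum. It does not depend on why 13% was printed; 3% is the most likely intended value.

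This should be fixed because it is the only stated precision for the primary estimate and it errs in the favourable direction. It is not a design flaw: the sample size, the safety monitoring and the final estimates from observed data are unaffected.

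**What to change.** **Minimum.** If the normal approximation was intended, change the interval in Section 8.0 to 3% to 37% and name that method.

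**Preferred.** Replace the sentence with one that states the count, the method and the result, for example: *If 3 of 15 patients in a stratum fail (20%), the exact (Clopper-Pearson) 90% confidence interval is 6% to 44%.* With Wilson the limits are 8% to 41%. Name the same method for the final stratum intervals. Exact suits a plan that wants coverage never below 90%, at the price of wider intervals; Wilson suits one that wants average coverage close to 90%. Either is sound, provided it is fixed before the data are analysed. Wald is the weakest choice at n = 15 because of its 81.5% coverage at the anticipated rate.

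**Cost.** One sentence of wording and a less favourable statement of precision. No extra patients, and no change to the strata or the stopping rule.
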